- **Prevalent patients:** Children who were already treated with Norditropin® before their inclusion in the study and who did not finish their growth upon their inclusion. For these patients, data will be collected both retrospectively and prospectively

HRQoL data will be collected on incident patients only. The inclusion period will last for 24 months and patients will be followed-up for 4 years, with possibility of extension for patients who did not reach adult height. This will allow to provide interim results on October 2025 to the French National Authority for Health (HAS). A total of 9 visits (1 inclusion visit: D0 and 8 follow-up visits: M6, M12, M18, M24, M30, M36, M42, M48) are planned. Each visit is allowed within one-month window. All information will be collected as per physicians' routine of care.

The design of the registry is displayed below :

Eligibility criteria .

Inclusion criteria

- Patients with a clinical and/or genetic diagnosis of NS
- Patients who are treated with Norditropin® (already treated or initiating) and who are followed in a participating centre
- The decision to initiate treatment with commercially available Norditropin® has been made by the patient/parents/Legally Acceptable Representative (LAR) and the treating physician before and independently from the decision to include the patient in this study.

Exclusion criteria

For an eligible patient, all exclusion criteria must be answered “no”.

- Patients/Parents/LAR opposed to the collection and processing of their children’s medical data.
- Mental incapacity, unwillingness or language barriers precluding adequate understanding or cooperation

Withdrawal criteria

- Patient withdrawal (opposition)
- Lost to follow-up
- Death

Key assessment variables

Norditropin[®] treatment patterns

- Date at start (baseline)
- Dose at Norditropin[®] treatment start in mg/kg/day (baseline)
- Date at the end of treatment (at one of the follow-up visit)
- Dose of Norditropin[®] in mg/kg/day at the end of follow-up (at one of the follow-up visit)

Auxological characteristics

- Age at gestational age in weeks (baseline)
- Weight at birth, 1 year, 2 years and 3 years of age in kg (baseline)
- Length at birth, 1 year, 2 years and 3 years of age in cm (baseline)
- Head circumference at birth, 1 year, 2 years and 3 years of age in cm (baseline)
- Mother’s height in cm (baseline)
- Father’s height in cm (baseline)
- Adult height (AH) in SDS (at one of the follow-up visit)

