Health-Related Quality of Life

- PedsQL score (from baseline until end of follow-up)

Data sources

The data required to address the registry objectives come from the medical records, prescription records, laboratory and questionnaires administered to patients (patient reported outcomes-PROs). Study investigators (or clinical research associates (CRAs) will capture data through an e CRF.

HRQoL will be collected directly from incident patients and their parents by using a self-administered validated quality of life questionnaire (PedsQL).

- **Number of patients to be studied**

According to experts' input, a maximum of 50 eligible incident patients could be included during the 24 months inclusion period. It is expected that the number of eligible patients initiating Norditropin[®] before 2020 would be lower since that there was no market authorisation for this indication yet and would not exceed 30 patients per year. Considering that eligible prevalent patients initiated Norditropin[®] from 2010, that 79% of solicited sites will be participating in the study (30 sites over 38) and that 80% of eligible patients will be included (excluding opposition, patient not regularly followed by this site), it is estimated that a maximum of 221 patients will be included in the registry.

Finally, the proportion of evaluable patients for the primary criteria (patients that have height measurements until the end of their 4 years follow-up or until they reach adult height (AH)) is planned to be 80%. Therefore, it is estimated that this study will enrol a maximum of 177 patients evaluable for the primary criteria.

Data analysis

There are 3 patients population considered in this study:

- Overall population: All patients included in the eCRF.
- Full Analysis Set (FAS): All patients included in the eCRF and meeting all selection criteria. All secondary analyses will be performed on FAS.
- Growth Analysis Set (GAS): All patients from the FAS for which the primary criteria can be evaluated, i.e. height measurements available until the end of the 4-year follow-up or AH is reached, whatever occurs first.

A descriptive analysis will be conducted on all study endpoints for which data has been collected both on FAS (GAS for primary endpoint) and per subgroups of interest as long as that the sizes of the subgroups are relevant for statistical estimations.

4 Amendments and updates

None.

5 Milestones

Table 1 Milestones

Milestone	Planned date

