7.1 Primary objective

The primary objective is to describe the long-term change of height in children treated with Norditropin[®] for short stature due to NS over a 4-year period* in routine clinical practice in France.

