8.2.3 Study population

Planned number of patients to be included: 224

Planned number of patients to complete the study: 168

Planned time period for the study: 24 months inclusion period and 4 years follow-up (with possibility of extension for patients who did not reach their adult height)

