8.2.8 Visit procedures

8.2.8.1 Study flow chart

Table 9 Study flow-chart

	Baseline (M0)	M6	M12	M18	M24	M30	M36	M42	M48
Inclusion/Exclusion criteria	X								
Socio-demographic characteristics									
Year of birth	X								
Sex	X								
Education, school level and educational measures	X	X	X	X	X	X	X	X	X
Clinical characteristics									
Age of onset of puberty	X								
Date of onset of menstruations (female only)	X								
Tanner stage	X	X	X	X	X	X	X	X	X
Comorbidities of interest not related to NS	X								
Pulse rate	X	X	X	X	X	X	X	X	X
Blood pressure (diastolic, systolic)	X	X	X	X	X	X	X	X	X
Echocardiogram parameters	X		X		X		X		X
Corrected QT interval (QTc) (measured by electrocardiogram (ECG))	X		X		X		X		X
Complete blood count (CBC)	X	X	X	X	X	X	X	X	X
Haemostasis parameters	X								
IGF-1 level	X	X	X	X	X	X	X	X	X
IGFBP-3 level	X								
TSH level	X								
FT4 level	X								
HbA _{1c} level	X		X		X		X		X
Fasting insulin blood level	X		X		X		X		X
Fasting glucose blood level	X		X		X		X		X
Fasting total cholesterol	X		X		X		X		X

	Baseline (M0)	M6	M12	M18	M24	M30	M36	M42	M48
Fasting triglycerides	X		X		X		X		X
Fasting HDL level	X		X		X		X		X
Fasting LDL level	X		X		X		X		X
Fasting Ratio total cholesterol/ HDL level	X		X		X		X		X
Parameters of gonadal function (inhibin B, AMH, LH, FSH, oestradiol / testosterone)	X		X		X		X		X
NS characteristics									
Auxological characteristics									
Gestational age at birth	X								
Head circumference at birth, at 1 year, at 2 years and 3 years of age	X								
Weight at birth, at 1 year, at 2 years and 3 years of age	X								
Length at birth, at 1 year, 2 years and 3 years of age	X								
Height velocity in the first year/ 6 months preceding Norditropin® start	X								
Weight at Norditropin® start	X	X	X	X	X	X	X	X	X
Height at Norditropin® start	X	X	X	X	X	X	X	X	X
Father 's height	X								
Mother's height	X								
Adult height (NAH)	X								
Bone age	X		X		X		X		X
Diagnosis									
Familial form of Noonan	X								
Parent affected	X								
Age of clinical diagnosis of NS	X								
Date of molecular diagnosis	X								
Molecular diagnosis (Type of NS-related genes mutated, and variant identified)	X								
NS comorbidities									

	Baseline (M0)	M6	M12	M18	M24	M30	M36	M42	M48
NS comorbidities	X	X	X	X	X	X	X	X	X
Therapeutic care									
Norditropin® treatment patterns									
Date of start	X								
Dose at start	X								
Dose titration		X	X	X	X	X	X	X	X
Dose at the end of treatment		X							

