8.2.10 Other assessments

Socio-demographic characteristics

- Sex (baseline)
- Age at start of Norditropin[®] treatment in years (baseline)

Clinical characteristics

- Age at puberty onset (at baseline or one of the follow-up visit)
- Age at onset of menstruations (female only) (at baseline or one of the follow-up visit)
- IGFBP-3 level (baseline)
- TSH level (baseline)
- FT4 level (baseline)
- Haemostasis parameters

Norditropin[®] treatment patterns

- Date at start (baseline)
- Dose of Norditropin[®] at treatment start in mg/k/day (baseline)
- Date at the end of treatment (at one of the follow-up visit)
- Dose of Norditropin[®] in mg/k/day at the end of follow-up (at one of the follow-up visit)

GH treatment history

- Type and number of previous GH treatments (baseline)
- Duration of GH treatment before Norditropin[®] in years (baseline)
- Dose of GH treatment before Norditropin[®] in mg/kg/day (baseline)
- Type of GH treatment following Norditropin[®] (at one of the follow-up visit)
- Date of start of GH treatment following Norditropin[®] (at one of the follow-up visit)
- Dose of GH treatment following Norditropin[®] in mg/kg/day (at one of the follow-up visit)

Auxological characteristics

- Age at gestational age in weeks (baseline)
- Weight at birth, 1 year, 2 years and 3 years of age in kg (baseline)

- Length at birth, 1 year, 2 years and 3 years of age in cm (baseline)
- Head circumference at birth, 1 year, 2 years and 3 years of age in cm (baseline)
- Height velocity in the first year/six months preceding Norditropin® treatment start
- Mother's height in cm (baseline)
- Father's height in cm (baseline)
- AH in SDS (at one of the follow-up visit)

Diagnosis

- Familial form of Noonan (baseline)
- Parent affected (baseline)
- Age of clinical diagnosis of NS (baseline)
- Molecular diagnosis performed (at one of the follow-up visit)
- Date of molecular diagnosis (at one of the follow-up visit)
- Molecular diagnosis (type of NS-related genes mutated, and variant identified) (at one of the follow-up visit)

NS comorbidities

- Type and number of NS comorbidities (baseline)

Health-Related Quality of Life (PROs): PedsQL

HRQoL will be assessed on incident patients only. They will be asked and their parents to complete the PedsQL questionnaire annually.

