8.5 Study sample size

This study will set up a registry that aims to include all eligible patients treated by Norditropin® for short stature due to Noonan syndrome.

No sample size calculation is required as this registry aims to include all patients fulfilling the sets of selection criteria defined.

According to experts' input, a maximum of 50 eligible incident patients could be included during the 24 months inclusion period. It is expected that the number of eligible patients initiating Norditropin® before 2020 would be lower since that there was no market authorisation for this indication yet and would not exceed 30 patients per year. Considering that eligible prevalent patients initiated Norditropin® from 2010, that 79% of solicited sites will be participating in the study (30 sites over 38) and that 80% of eligible patients will be included (excluding opposition, patient not regularly followed by this site), it is estimated that a maximum of 221 patients will be included in the registry.

Finally, the proportion of evaluable patients for the primary criteria (patients that have height measurements until the end of their 4 years follow-up or adult height) is planned to be 80%. Therefore, it is estimated that this study will enrol a maximum of 177 patients evaluable for the primary criteria.

The height variation (in SDS) after 4 years of treatment has been evaluated in the ANSWER® Program (observational study) at 1,14 (0,13) SDS. The change in height SDS is estimated with a 11,4% coefficient of variation (ratio of standard deviation over mean).

The following table presents the precision in primary criteria measurement (with a 2-sided 95% confidence interval (CI)) for the estimation of mean height variation in SDS considering a 20% coefficient of variation. The primary criteria will be estimated with a 2.95% precision. This high level of precision enables to perform subgroup analysis with also a satisfying precision.

Table 11 Precision of the primary criteria depending on the number of evaluable patients

Sample size	150	160	170	177	190	200
Precision for 95% CI	3.2%	3.1%	3.0%	2.95%	2.85%	2.78%

The sample size (n) is calculated based on the normal approximation using the following formula:

$$N = z_{1-\alpha/2}^2 \frac{cv^2}{\epsilon^2}$$

where:

- z is the standard normal distribution's quantile (for $\alpha=5\%$),
- CV is the coefficient of variation (20%),

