8.7 Data analysis

8.7.1 Definition of analysis sets

The site populations will be defined as follows:

- Contacted sites: all reference and competence centres in France will be solicited to participate in this study
- Participating sites: all sites that agreed to participate in the study
- Active sites: all sites that included at least one eligible patient

The sites main characteristics (localisation, size) will be compared to ensure that the active sites are representative at the national level.

There are 3 patients population considered in this study:

- Overall population: all patients included in the eCRF,
- Full Analysis Set (FAS): all patients included in the eCRF and meeting all selection criteria. All secondary analyses will be performed on FAS.

- Growth Analysis Set (GAS): all patients from the FAS for which the primary criteria can be evaluated, i.e. height measurements available until the end of the 5-year follow-up or until NAH is reached, whatever occurs first.

The subgroups of interest for analyses are defined as follows:

- Norditropin[®] treatment duration: depending on age of onset and age at puberty onset, the patients may have shorter or longer time under GH treatment, which may highly influence auxological outcomes
- Mutated gene: PTPN11, SOC2, other

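### Section 8.7.1 defines the primary-analysis set by a 5-year follow-up, while the rest of the protocol plans, sizes and schedules 4 years

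*Protocol*

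**What the plan says.** Section 8.7.2 assigns the primary endpoint, change in height SDS, to the Growth Analysis Set (GAS). The protocol defines that set twice:

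- Section 8.7.1: patients of the Full Analysis Set with "height measurements available until the end of the 5-year follow-up or until NAH is reached, whatever occurs first".
- Abstract, Data analysis: patients with "height measurements available until the end of the 4-year follow-up or AH is reached, whatever occurs first".

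Section 8.5, the source of the 177 evaluable patients, counts "patients that have height measurements until the end of their 4 years follow-up or adult height". The primary objective in 7.1 is set "over a 4-year period* in routine clinical practice in France". Section 8.2.3 plans "24 months inclusion period and 4 years follow-up (with possibility of extension for patients who did not reach their adult height". Section 8.1 schedules the last visit at M48.

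The growth end point also changes name. It is AH in the abstract, adult height in 8.5 and NAH in 8.7.1, and Table 9 joins both terms in a row labelled "Adult height (NAH". NAH is expanded in the abbreviation list, but no distinction from AH is given. Section 8.7.2.1 ends the primary endpoint at the end of follow-up or at GH, which is the abbreviation for growth hormone and not a time point as it stands. Section 8.7.3 sends the interim analysis back to 8.7.2.1.

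**The concern.** The GAS decides whose height changes make up the primary result. An incident child starts Norditropin at inclusion and so has 4 years of on-treatment heights at M48. Under 8.7.1 as written, that child enters only if near adult height has been reached or follow-up has been extended to 5 years.

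A prevalent child is placed differently. Heights are collected from the records back to treatment start, so 5 years may already exist, and a child who has finished growing qualifies through the height route. Any exclusion would therefore follow patient group. Incident children are the group observed prospectively from treatment start, whereas 8.5 says that patients starting before 2020 did so without a marketing authorisation for this indication.

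The 177 evaluable patients and the 2.95% precision in 8.5 also belong to the 4-year rule. The protocol gives no evaluable number for a 5-year rule. Separately, the interim report of October 2025 uses the same primary analysis, and its date has to be set against the earliest possible M48.

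**Working it through.** **1. The places that fix the rule**

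| Place | Follow-up | Growth end point |
|---|---|---|
| Abstract, GAS | 4 years | AH |
| 7.1 objective | 4 years | – |
| 8.1 schedule | last visit M48 | – |
| 8.2.3 | 4 years, extension possible | adult height |
| 8.5 evaluability | 4 years | adult height |
| Table 1 | March 2024 to March 2028 = 4 years | – |
| **8.7.1, GAS** | **5 years** | **NAH** |

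Section 8.7.1 is the only place with a 5-year follow-up.

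**2. The plan's own figures**

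Inputs from 8.5: 50 incident patients; at most 30 prevalent patients per year from 2010; 79% of sites; 80% of eligible patients included; 80% evaluable; coefficient of variation (CV) 20%. The number of prevalent years is not stated. Ten years (2010–2019) is my assumption.

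- Included: (50 + 30 × 10) × 0.79 × 0.80 = 221.2 (stated 221). Eleven years would give 240.
- Evaluable: 221 × 0.80 = 176.8 (stated 177).
- Precision: 1.96 × 0.20 / √177 = 2.946% (stated 2.95%).

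All three reproduce, so they rest on the 4-year/adult-height rule.

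**3. Ceiling on the patients exposed**

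- Incident, included: 50 × 0.79 × 0.80 = 31.6.
- Incident, evaluable: 31.6 × 0.80 = 25.3, and 25.3 / 177 = 14%.

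If the 50 were already the included number, 50 × 0.80 = 40 would be exposed. The total would then be 50 + 300 × 0.79 × 0.80 = 239.6, which does not match 221, so I use 25.

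**4. Effect on precision (CV 20% as in the plan)**

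The share of incident children actually lost is not given, so the range is:

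| Evaluable incident children lost | GAS | Precision |
|---|---|---|
| none | 177 | 2.95% |
| half | 164 | 3.06% |
| all | 152 | 3.18% |

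**5. Room for extension**

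Five prospective years by March 2028 require inclusion by March 2023. That covers 12 of the 24 inclusion months (March 2022 to March 2024). Children included later cannot reach 5 years within the planned dates.

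**6. Interim report**

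- First inclusion March 2022 + 48 months = March 2026, after October 2025.
- March 2022 to October 2025 = 43 months, the longest possible incident follow-up.
- Last inclusion March 2024 + 12 months = March 2025, so every incident child still followed can have M12 before the report.

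**The case against.** The strongest reply is that the 5-year phrase is a single slip, with 4 years stated everywhere else, and that an analyst would read it as 4. That is probably how it arose. It nevertheless stands in the section that defines the analysis sets, and the only competing definition of the GAS is in the abstract, so the correction is still needed.

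Several stronger readings are tempting, and the documents do not support them:

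- *All incident children drop out.* Extension is open to those who have not reached adult height, and the near-adult-height route remains. The 25 is a ceiling.
- *The error makes the primary result rest on retrospective patients.* On the planning figures, 300 of 350 eligible patients (86%) are prevalent under either rule. The 5-year wording would tilt the set further but does not create the imbalance.
- *Prevalent children who are still growing are lost too.* This needs a clock that starts at inclusion. Table 2 runs the endpoint from treatment start, and 8.1 collects these children's earlier data.
- *Adult height cannot be identified because Table 9 marks it only at baseline.* The single mark may be a merged cell flattened in text extraction. Height is marked at every visit, and 8.2.10 records "AH in SDS (at one of the follow-up visit".
- *No primary analysis is possible in October 2025.* Prevalent patients, with treatment starts from 2010, can meet the rule by then, and incident children appear in the secondary analyses on the Full Analysis Set.
- *A set of completers requires a mixed model as the primary analysis.* This is a descriptive registry, and section 8.9.1 acknowledges attrition with measures against it. Replacing the primary analysis would be a redesign, and the contradiction does not demand it.

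**Conclusion.** The contradiction is real and concerns the set used for the primary endpoint. Taken literally, 8.7.1 excludes incident children followed only to M48 without near adult height. That is at most about 25 of 177 (14%), with precision going from 2.95% to at most about 3.18%. These figures assume ten prevalent recruitment years, the inclusion factors of 8.5 applied equally to incident and prevalent patients, and the plan's CV of 20%. The true loss could be anywhere from none to that ceiling.

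The numerical effect is small. What matters is that the protocol gives two rules for entry to the primary analysis, that the one in 8.7.1 has no evaluable number behind it, and that any loss would fall selectively on incident children.

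The timing point holds in a narrow form and survives the change to 4 years: in October 2025 no incident child can have M48, so only one who has reached adult height can be in the primary analysis.

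**What to change.** 1. In 8.7.1, replace the 5-year follow-up with 4 years.
2. Choose one term, AH or NAH, define it once, and use it in the abstract, Table 9, 8.5 and 8.7.1. The visit marks in Table 9 need not change for this point.
3. State that the 4 years run from the start of Norditropin, in line with Table 2.
4. In 8.7.2.1, replace the GH cut-off with the same end point as in 8.7.1.
5. In 8.7.3, state that the October 2025 primary analysis can include no incident child who has not reached adult height. Report the change in height SDS of incident children descriptively at visits already reached, for example M12.

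The cost is wording in five places and one descriptive interim table. No data collection is added, and the stated 177 and 2.95% stand unchanged.

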8.1.1.2 Secondary endpoints

Secondary objective-1: To evaluate the long-term safety profile of Norditropin®.

All drug related adverse reactions (ADR), serious adverse drug reactions (SADR), serious adverse events (SAE) and adverse events (AE) will be recorded and described up to the end of growth development or end of follow-up if earlier. The endpoints related to the secondary objective-1 are listed in [Table 3](#).

Table 3 Secondary endpoints in relation to secondary objective 1

Title of endpoint	Time frame	Unit
Number of adverse drug reactions (ADR)	From start of Norditropin® until end of follow-up	Count of events
Number of serious adverse drug reactions (SADR),	From start of Norditropin® until end of follow-up	Count of events
Number of serious adverse events (SAE)	From start of Norditropin® until end of follow-up	Count of events
Number of adverse events (AE)	From start of Norditropin® until end of follow-up	Count of events

Secondary objective-2: To describe the socio-demographic and clinical characteristics of patients. The endpoints related to the secondary objective-2 are listed in [Table 4](#).

Table 4 Secondary endpoints in relation to secondary objective 2

Title of endpoint	Time frame	Unit
Socio-demographic		
Education	From start of Norditropin® treatment until end of follow-up	NA
School level	From start of Norditropin® treatment until end of follow-up	NA
Educational measures	From start of Norditropin® treatment until end of follow-up	NA
Clinical characteristics		

Title of endpoint	Time frame	Unit
Tanner stage	At all visits	NA
Change in pulse rate	From start of Norditropin® treatment until end of follow-up	Beats per minute
Change in diastolic blood pressure	From start of Norditropin® treatment until end of follow-up	mm Hg
Change in systolic blood pressure	From start of Norditropin® treatment until end of follow-up	mm Hg
Change in corrected QT-interval (Electrocardiogram)	From start of Norditropin® treatment until end of follow-up	msec
Change in echocardiogram parameters	From start of Norditropin® treatment until end of follow-up	mm (Left ventricular interventricular septal maximum thickness in diastole) mm (Left ventricular end diastolic diameter) % (Left Ventricular Fractional Shortening (LVFS)) % (Left Ventricular Ejection Fraction (LVEF)) Cm/s (Diastolic function (Ea)) Cm/s (Diastolic function (Aa))

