8.7.2 Statistical methods

A descriptive analysis will be conducted on all study endpoints for which data has been collected both on FAS (GAS for primary endpoint) and per subgroups of interest as long as that the sizes of the subgroups are relevant for statistical estimations.

The following statistics will be provided for quantitative variables: number of patients with non-missing and missing values, mean, standard deviation, median, first quartile (Q1), third quartile (Q3), minimum and maximum value, mode (for discrete quantitative variables with limited variability).

For qualitative variables, the number and proportion of each variable modality will be provided together with the number of missing values. Proportions will be computed based on the population with non-missing data. Missing data will not be imputed or replaced.

Exploratory comparison between study subgroups might be considered. Statistical tests will be based on the type and the variables. All comparison tests will be two-tailed with a standard type 1 error threshold of 5% (significance level).

In order to reach the exploratory objectives, logistic regressions will be implemented to identify factors linked to Norditropin[®] growth evolution (reaching height > -2 SDS) and patients' HRQoL. The clinically relevant explanatory variables will be first tested with univariate regression. The selected variables will be processed in the multivariate regression (backward selection) and the odds-ratio with their 95% confidence interval will be used for interpretation when the variable effect is significant (5% threshold for p-value).

In addition, a mixed model will be developed to explore HRQoL scores evolution over the follow-up. Patient effect will be considered as random effect.

The patients will be enrolled in the study over a variable period limited to 24 months. The probability that a patient is included in the cohort is greater when the patient has a higher number of annual visits. This study design therefore presents several biases related to:

- the heterogeneous duration of patients' inclusion which depends on the activity size of each participating site;

- the probability that a patient is included in the cohort which depends on the frequency of annual visits.

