8.7.4 Sequential safety analysis/safety monitoring

All drug related adverse reactions (ADR), serious adverse drug reactions (SADR), serious adverse events (SAE) and adverse events (AE) will be classified and analysed from the initiation of the study drug until the end of follow-up.

Medical Dictionary for Regulatory Activities (MedDRA) version 19.1 or higher will be used for coding to "Lower Level Term (LLT)", "Preferred Term (PT)", "High Level Term (HLT)", "High Level Group Term (HLGT)" and the associated primary "System Organ Class (SOC)". CTCAE version 5 will be used to provide the grade.

AEs will be analysed as follows:

The number and percentage of patients experiencing:

- at least 1 on-treatment SAE/AE/SADR/ADR (including non-serious and serious irrespective of the relationship with the study treatment)
- at least 1 on-treatment SAE/AE/SADR/ADR related to the study treatment (including serious and non-serious AEs)
- at least 1 on-treatment serious SAE/SADR (regardless the relationship with the study treatment)
- at least 1 on-treatment serious SAE/SADR related to the study treatment
- at least 1 on-treatment SAE/AE/SADR/ADR leading to treatment discontinuation
- at least 1 on-treatment SAE/AE/SADR/ADR leading to treatment interruption/delay
- at least 1 on-treatment SAE/AE/SADR/ADR leading to dose decrease
- fatal on-treatment SAE/AE/SADR/ADR

They will be presented by SOC and preferred term.

Patient will be counted once by AE taking into account the maximum grade. The SOC/PT will be summarized (irrespective of the grade) and by maximum grade CTCAE (grade 1-2 ,3-4 and 5) as well. The incidence rate, corresponding to the number of patients experiencing at least one AE divided by the total person years of follow-up, will be calculated for each AE. A listing will be provided for fatal on-treatment AE. These analyses will be performed for the post-treatment AEs as well.

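### On-treatment adverse-event percentages are not comparable across subgroups of realised Norditropin duration, yet section 8.7.2 applies those subgroups to every endpoint

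*Protocol*

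**What the plan says.** Section 8.7.1 lists two subgroups of interest, of which the first is Norditropin treatment duration. It explains that "depending on age of onset and age at puberty onset, the patients may have shorter or longer time under GH treatment". The only consequence it names is for growth: "which may highly influence auxological outcomes". No safety reason is given.

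Section 8.7.2 states: "A descriptive analysis will be conducted on all study endpoints for which data has been collected both on FAS", with the growth set used for the primary endpoint, and "per subgroups of interest as long as that the sizes of the subgroups are relevant for statistical estimations". Subgroup size is the only condition. It adds: "Exploratory comparison between study subgroups might be considered", with two-sided tests at 5%. Section 8.7.2.2 sends all secondary endpoints to these methods.

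The counts of AEs, SAEs, ADRs and SADRs are secondary endpoints (section 8.1.1.2, Table 3), with the time frame "From start of Norditropin® until end of follow-up".

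Section 8.7.4 tabulates numbers and percentages of patients with on-treatment events, one row being "at least 1 on-treatment SAE/AE/SADR/ADR leading to treatment discontinuation". It also defines an incidence rate: patients with at least one AE over total person-years of follow-up. The analyses are repeated for post-treatment AEs. Table 10 (section 8.3) lists safety among the reasons for a treatment modification and permanent stop among the types.

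**The concern.** Duration is known only after treatment has run its course, so a subgroup defined by it is not a baseline subgroup. For on-treatment harms this matters in two ways.

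- **Unequal windows.** An on-treatment event can be counted only while the child is treated. Grouping by treatment duration therefore also groups by length of exposure to being counted.
- **Event-driven membership.** A child whose treatment ends permanently because of an AE is thereby placed in a shorter-duration group.

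The first effect makes longer treatment look worse; the second makes shorter treatment look worse. Neither needs duration to have any real effect. The registry has no control group and answers an authority's request for long-term safety data (section 6.2), so harm by length of exposure is a contrast readers will look for. A table built this way could alarm or reassure without cause.

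**Working it through.** **Inputs.** The protocol gives no figure for safety by subgroup. The event rate λ, the durations and the probability q that an AE permanently stops treatment are all assumptions. Throughout, the AE hazard is constant and duration has no true effect.

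**The plan's own cohort size.** Section 8.5: (50 + 30 × 10) × (30/38) × 0.80 = 221.1, matching the stated 221. On these inputs 300/350 = 86% of eligible children are prevalent, which matters in step 5.

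**1. Window effect alone (q = 0).** P(at least one on-treatment event) = 1 − exp(−λT).

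| λ per year | T = 4 years | T = 8 years |
|---|---|---|
| 0.05 | 18.1% | 33.0% |
| 0.10 | 33.0% | 55.1% |
| 0.30 | 69.9% | 90.9% |

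**2. Adding event-driven stopping.** Simulation with 221 children, 1,000 runs per scenario, intended duration uniform on 1–8 years, groups split at 4 years of realised duration, λ = 0.10. The last two columns give the share of runs significant at the two-sided 5% level in each direction.

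| q | <4 years | ≥4 years | False: longer is worse | False: shorter is worse |
|---|---|---|---|---|
| 0 | 21.8% | 45.0% | 95% | 0% |
| 0.1 | 25.8% | 42.6% | 74% | 0% |
| 0.3 | 31.9% | 37.7% | 13% | 0.3% |
| 0.5 | 36.9% | 32.5% | 0.6% | 10% |
| 1 | 45.7% | 17.6% | 0% | 99.6% |

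The sign reverses as q rises, and between about 0.3 and 0.5 the two effects nearly cancel. With q = 0, a false result that longer is worse appears in 76% of runs at λ = 0.05 and 99.9% at λ = 0.30.

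**3. The planned incidence rate.** Apply the section 8.7.4 definition to on-treatment AEs, with 4 years of follow-up for everyone and 2 or 4 years on treatment, λ = 0.10, q = 0:

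- 2 years: (1 − exp(−0.2))/4 = 0.181/4 = 0.045 per person-year
- 4 years: (1 − exp(−0.4))/4 = 0.330/4 = 0.082 per person-year

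The ratio is 1.8 (1.96 at λ = 0.02 and 1.55 at λ = 0.30). Replacing the denominator by on-treatment person-years, and counting all events, removes the window effect when q = 0 (0.099 against 0.101). It does not when events stop treatment: at q = 0.3 the result is 0.152 in the short group and 0.080 in the long group, where the truth is 0.100 in both.

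**4. Time-since-start bands.** Split each child's treated time at 4 years, and divide events in each band by person-years in that band. In a simulation of 400,000 children with λ = 0.10, over q = 0 to 1, the rates are 0.100 in the 0–4 year band and 0.099 to 0.101 in the later band. The artefact disappears for every q.

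**5. A condition on step 4.** Section 10.1 starts AE collection at informed consent, whereas Table 3 and section 8.7.4 start at Norditropin initiation. Suppose a prevalent child started 5 years before inclusion, stays on treatment for 4 more, and earlier AEs are not captured. With λ = 0.10, the 0–4 year band then holds 4 person-years and no recorded events. The later band holds 5 person-years and 0.10 × 4 = 0.4 expected recorded events, a rate of 0.08. Late exposure looks worse only because early events went unrecorded. Person-time must therefore be counted only while AEs were ascertained.

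**The case against.** The link to safety is indirect. The duration subgroup is justified by growth, section 8.7.2.1 names duration for the primary endpoint only, and section 8.7.4 mentions no subgroups. How safety is tabulated by subgroup could be left to the SAP. This limits the point but does not remove it: section 8.7.2 says all study endpoints will be described by subgroup, safety counts are among them, and a SAP following that text would produce these tables. Testing, however, is only a possibility, and no test of harms is named.

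Several stronger readings are tempting and not supported:

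- *Percentages will always show more harm with longer treatment.* Step 2 shows that the direction depends on q, which the documents do not give.
- *Every per-person-year rate will show less harm with longer treatment.* With the follow-up denominator that section 8.7.4 defines, longer can look worse (0.045 against 0.082).
- *The artefact is about ten-fold.* A figure of that size (0.048 against 0.005 per on-treatment person-year) arises only for AEs leading to discontinuation, the row tied to duration by its definition. It also needs a denominator that section 8.7.4 does not define, and assumptions of λ = 0.10, 10% of AEs ending treatment and intended durations uniform on 1–12 years.
- *The Table 3 counts are on-treatment counts.* They run to the end of follow-up.
- *Duration is generally determined by events.* Only an AE that permanently stops treatment has this effect; section 8.7.1 attributes duration to age at onset and at puberty.

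For prevalent children, the recorded event window may also differ from treatment duration if AE collection starts at inclusion. Table 10 runs total duration to the end of follow-up, so its end point is not settled either. Both facts blur the size of the window effect; neither makes the groups comparable.

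**Conclusion.** The concern holds in this form: read as written, sections 8.7.1, 8.7.2 and 8.7.4 lead to on-treatment AE percentages by realised Norditropin duration, and these do not support comparison between the groups. A spurious association can arise in either direction, and at some stopping probabilities the two effects roughly cancel. The window effect follows from the definitions wherever AEs are recorded throughout treatment; every size quoted rests on the assumed rates, durations and stopping probabilities. The planned incidence rate does not correct the problem. The growth analyses by duration are not affected by this point. It should be corrected before safety tables are specified, but it does not bear on the primary endpoint.

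**What to change.** In sections 8.7.1 and 8.7.2, restrict the total-duration subgroup to growth endpoints, and state that harms will be neither described nor tested by total duration.

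In section 8.7.4, report on-treatment events per person-year with 95% confidence intervals by time since Norditropin start, for example 0–1, >1–2, >2–4 and >4 years. Each child contributes events and person-time to every band passed through while on treatment.

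Count person-time only over the period in which AEs were actually ascertained. If AEs before inclusion are not captured, prevalent children should enter late, at their time since start on the day of inclusion. Section 10.1 must be reconciled with Table 3 and section 8.7.4 on when AE collection begins; until then the entry time cannot be fixed.

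The cost is protocol and SAP wording plus one split of person-time. Treatment start and end dates are already collected; whether AEs before inclusion are available depends on that reconciliation. The downside is wider intervals in sparsely filled bands.
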